11.6 Tango Confidence Interval

Two proportions from the same sample of observations or from matched-pair samples are correlated. McNemar's test (McNemar, 1947) is commonly conducted to test the equivalence of two correlated proportions ([Table 6](#)).

Table 6: Contingency Table of Seroconversion Rate

		2019nCoV-312		Total
		SCR (Yes)	SCR (No)	
2019nCoV-307	SCR (Yes)	a (π_{11})	b (π_{12})	a + b (π_{1+})
	SCR (No)	c (π_{21})	d (π_{22})	c + d (π_{2+})
	Total	a + c (π_{+1})	b + d (π_{+2})	n

Testing the null hypothesis $\pi_{1+} - \pi_{+1} = 0$ is equivalent to testing $\pi_{12} - \pi_{21} = 0$. Given the null hypothesis, the McNemar's test statistic (Chi-squared) can be computed as follows:

$$\chi^2 = (b - c)^2 / (b + c)$$

where

b is the frequency of participants who has seroconversion rate before booster dose but don't have seroconversion rate after booster dose, and

c is the frequency of participants who don't has seroconversion rate before booster dose but have seroconversion rate after booster dose

Under the null hypothesis, the McNemar's statistic follows an asymptotic chi-square distribution with one degree of freedom when b + c is greater than 10.

The confidence interval for the difference in two correlated proportions ($\lambda = \pi_{1+} - \pi_{+1} = \pi_{12} - \pi_{21}$) developed by Tango is estimated by solving the following two equations iteratively until the change in estimation is infinitesimal below the predetermined cutoff.

$$\frac{b-c-n\lambda}{\sqrt{n(2\hat{\pi}_{21}+\lambda(1-\lambda))}} = \pm z_{\alpha/2}$$

Where

λ is the difference between two correlated proportions, and

$\hat{\pi}_{21}$ is estimated as

$$\hat{\pi}_{21} = \frac{\sqrt{(B^2 - 4AC) - B}}{2A}$$

Where

$$A = 2n$$

$$B = -b - c + (2n - b + c)\lambda, \text{ and}$$

$$C = -c\lambda(1 - \lambda)$$

Although the computational procedures for Tango's CI are more complex, the upper and lower limits are easily found through the Secant method with empirically good coverage probabilities ([Newcombe, R. G. 1998](#)) and can be applied to small samples with off-diagonal zero cells [Tango, T. 1998](#)).

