7 ANALYSES ADDRESSING PROTOCOL OBJECTIVES

7.1 Statistical Hypothesis

FoFor To evaluate the Nab responses to ancestral strain Novavax vaccine administered as a second (or subsequent) booster after licensed mRNA vaccines and a first ancestral strain Novavax vaccine booster, two statistical hypotheses will be evaluated in the group receiving **ancestral strain NVX-CoV2373.**

- Non-inferiority of a second (or subsequent) booster dose of NVX-CoV2373, as measured by the lower-bound (LB) of the 95% confidence interval (CI) for $GMR_{312/307}$ defined as the ratio of Nab Geometric Mean Titer (GMT) **28 days after a second (or subsequent) booster dose** of NVX-CoV2373 in Study **2019nCoV-312** versus **28 days after a first booster dose** of NVX-CoV2373 in Study **2019nCoV-307** among the same participants being > 0.67 . This is expressed statistically as:

$$\begin{aligned} H_0: GMR_{312/307} &\leq 0.67 \\ H_1: GMR_{312/307} &> 0.67 \end{aligned}$$

[figure not shown]
- Non-inferiority of a second (or subsequent) booster dose of NVX-CoV2373, as measured by the lower-bound (LB) of the 95% exact CI for the difference of proportion of participants with seroconversion (SCR) in Nab titers **28 days after a second (or subsequent) booster dose** of NVX-CoV2373 in Study **2019nCoV-312** relative to time of Day 1 dose in Study **2019nCoV-307** versus **28 days after a first booster dose** of NVX-CoV2373 in Study **2019nCoV-307** relative to time of Day 1 dose in Study **2019nCoV-307** among the same participants being $> -10\%$. This is expressed statistically as:

$$\begin{aligned} H_0: SCR_{312} - SCR_{307} &\leq -10\% \\ H_1: SCR_{312} - SCR_{307} &> -10\% \end{aligned}$$

Successful demonstration of non-inferiority of the booster dose requires lower-bound (LB) of the 95% confidence interval (CI) for $GMR_{312/307}$ defined as the ratio of Nab Geometric Mean Titer (GMT) **28 days after a second (or subsequent) booster dose** of NVX-CoV2373 in Study **2019nCoV-312** versus **28 days after a first booster dose** of NVX-CoV2373 in Study **2019nCoV-307** among the same participants being > 0.67 to meet the primary endpoint ([Figure 2](#)). If non-inferiority is demonstrated, successful demonstration of superiority being $GMR_{312/307} > 1.0$ will meet the primary endpoint.

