where, for n subjects, v_{ij} and v_{ik} are observed immunogenicity titers for subject i at time points j (28 days after a second (or subsequent) booster dose of NVX-CoV2373 in Study 2019nCoV-312) and k (28 days after a first booster dose of NVX-CoV2373 in Study 2019nCoV-307).

As the 1st secondary objectives of characterizing Nab response to ancestral strain Novavax vaccine administered as a second (or subsequent) booster after licensed mRNA vaccines and a first ancestral strain Novavax vaccine booster, the derived/calculated endpoints of Nab response for **the group receiving ancestral strain Novavax vaccine** will include:

- SCR is defined as proportion of participants who achieve seroconversion \geq 4-fold increase from baseline in Nab titers at Day 29 if the baseline value is equal to or above LLOQ or at least 4-fold fold rise from LLOQ if the baseline value is lower than LLOQ.

- SCR in Nab GMEUs with corresponding two-sided exact binomial 95% CIs will be calculated using the Clopper-Pearson method with the following sample SAS code:

```
proc freq data=Nab noint;
  tables seroconvind / binomial(exact) alpha=.05;
  output out=out1 binomial;
run;
```

- Two-sided 95% CIs of the difference in SCRs in Nab titers **28 days after a second (or subsequent) booster dose** of NVX-CoV2373 in Study **2019nCoV-312** relative to time of Day 1 dose in Study **2019nCoV-307** versus **28 days after a first booster dose** of NVX-CoV2373 in Study **2019nCoV-307** relative to time of Day 1 dose in Study **2019nCoV-307** among the same participants will be based on the method of confidence interval for the difference in two correlated proportions by Tango (SAP Section [11.6](#)). Non-inferiority will be demonstrated if the LB of the 95% exact CIs for the difference of SCRs ($SCR_{312} - SCR_{307}$) in Nab titers is higher than -10%.

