As the 3rd secondary objectives of characterizing the cross-reaction of neutralizing and IgG antibodies induced by the ancestral strain Novavax vaccine to more recent SARS-CoV-2 variants and any other variants for which appropriate assays are available, the derived/calculated endpoints of Nab response for **the group receiving updated Novavax COVID-19 Vaccine based on recent variant(s)** will include Nab GMTs at Days 1 and 29, $GMFR_{Post/Pre}$ (Day 29 vs. Day 1), $GMR_{312/307}$, SCRs (Day 29 vs. Day 1), and difference in SCRs ($SCR_{312} - SCR_{307}$) in Nab titers to be calculated using the same calculations and comparison periods as noted above for **the group receiving ancestral strain Novavax vaccine**.

Above parameters based on the Pseudovirus-based Nab response per Wuhan strain from Study 2019nCoV-307 tested by Monogram will be presented together with the summary of Study 2019nCoV-312 to evaluate the primary endpoints of Nab response.

Since the Pseudovirus-based Nab response (Wuhan) at 4 different visits including the date of 1st booster dose (Day 1 in 2019nCoV-307), 28 days after 1st booster dose (Day 29 in 2019nCoV-307), date of 2nd booster dose (Day 1 in 2019nCoV-312) and 28 days after 2nd booster dose (Day 29 in 2019nCoV-312) were tested using the similar Pseudovirus Neutralization Assay by two different labs of Monogram and NVX CI, below conversions will be applied to the individual value in the unit of ID50 to the value in the standard unit of IU/mL.

2019nCoV-307 (Monogram): $ID50 * 0.1458 = IU/mL$

2019nCoV-312 (NVX CI): $ID50 * 0.214 = IU/mL$ Pseudovirus-based Nab response (Omicron BA.5) of Study 2019nCoV-312 will be presented including GMT, $GMFR_{Post/Pre}$ and SCR.

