- Two-sided 95% CIs of the difference in SCRs in IgG GMEU **28 days after a second (or subsequent) booster dose** of NVX-CoV2373 in Study **2019nCoV-312** relative to time of Day 1 dose in Study **2019nCoV-307** versus **28 days after a first booster dose** of NVX-CoV2373 in Study **2019nCoV-307** relative to time of Day 1 dose in Study **2019nCoV-307** among the same participants will be based on the method of confidence interval for the difference in two correlated proportions by Tango (SAP Section [11.6](#)). Non-inferiority will be demonstrated if the LB of the 95% exact CIs for the difference of SCRs (SCR₃₁₂ – SCR₃₀₇) in IgG GMEUs is higher than –10%.

As the 3rd secondary objectives of characterizing the cross-reaction of neutralizing and IgG antibodies induced by the ancestral strain Novavax vaccine to more recent SARS-CoV-2 variants and any other variants for which appropriate assays are available, the derived/calculated endpoints of IgG response for **the group receiving updated Novavax COVID-19 Vaccine based on recent variant(s)** will include IgG GMEU at Day 1 and Day 29, GMFR_{Post/Pre} (Day 29 vs. Day 1), GMR_{312/307}, SCRs (Day 29 vs. Day 1), and difference in SCRs (SCR₃₁₂ – SCR₃₀₇) in

IgG GMEU to be calculated using the same calculations and comparison periods as noted above for the group receiving ancestral strain Novavax vaccine.

Please note above parameters of IgG data (Wuhan) from both studies of Study 2019nCoV-307 and 2019nCoV-312 will be presented together and above parameters of IgG data (Omicron BA.5) from both studies will be presented together to evaluate the secondary endpoints.

7.2.3 hACE2 Receptor-binding Inhibition Titers for SARS-CoV-2

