As the 4th secondary objectives of further characterizing antibody responses in a human angiotensin-converting enzyme 2 (hACE2) receptor binding inhibition assay to the SARS-CoV-2 ancestral strain spike protein, the derived/calculated endpoints of hACE2 response will include hACE2 GMTs at Day 1 and Day 29, GMFR_{Post/Pre} (Day 29 vs. Day 1), GMR_{312/307}, SCRs (Day 29 vs. Day 1), and difference in SCRs (SCR₃₁₂ – SCR₃₀₇) in hACE2 titers using the same calculations and comparison periods as noted above for neutralizing antibodies. Please note, SCR is defined as proportion of participants who achieve seroconversion \geq 4-fold increase from baseline in hACE2 titers at Day 29 if the baseline value is equal to or above LLOQ or at least 4-fold fold rise from LLOQ if the baseline value is lower than LLOQ.

Please note above parameters of hACE2 data (Wuhan) from Study 2019nCoV-307 will be presented together with the summary of 2019nCoV-312; hACE2 data (Omicron BA.5) of Study 2019nCoV-312 will be summarized including GMT, GMFR_{Post/Pre} and SCR.

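### SAP 11.6 computes the Tango interval for SCR307 − SCR312, but the −10% lower-bound rule in 7.2.1 and 7.2.2 is for SCR312 − SCR307, so both secondary SCR non-inferiority tests run backwards if 11.6 is used as written

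*SAP*

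**What the plan says.** **Hypothesis.** SAP 7.1 puts the alternative for the Nab seroconversion rate as "H_1: SCR_{312} - SCR_{307} &> -10"%, that is, second booster minus first.

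**Decision rules.** SAP 7.2.1 (Nab) bases the interval on "the method of confidence interval for the difference in two correlated proportions by Tango (SAP Section [11.6") and declares non-inferiority if the "LB of the 95% exact CIs for the difference of SCRs ($SCR_{312} - SCR_{307}$) in Nab titers is higher than -10"%. SAP 7.2.2 (IgG) repeats the pattern. It cites the "confidence interval for the difference in two correlated proportions by Tango (SAP Section [11.6") and applies the lower-bound rule to the same SCR312 − SCR307 difference, which passes if the bound "in IgG GMEUs is higher than –10"%.

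**Formula.** Protocol 9.3.2 leaves the details of the Tango method to the SAP, so SAP 11.6 is the only specification. Its Table 6 has Study 307 as rows and Study 312 as columns. The row margin is a + b (π₁₊) and the column margin is a + c (π₊₁). The interval is for the "difference in two correlated proportions ($\lambda = \pi_{1+} - \pi_{+1} = \pi_{12} - \pi_{21}$) developed by Tango", and the score equation has numerator b − c − nλ.

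**Borrowed uses.** For the updated-vaccine group, 7.2.1 asks for the "difference in SCRs ($SCR_{312} - SCR_{307}$) in Nab titers to be calculated using the same calculations and comparison periods as noted above", and 7.2.2 does the same for IgG. Section 7.2.3 asks for the SCR difference "in hACE2 titers using the same calculations and comparison periods as noted above for neutralizing antibodies".

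**The concern.** The section that defines the interval and the sections that apply the margin subtract in opposite orders. A lower bound compared with −10% means different things in the two directions. For SCR312 − SCR307 it asks whether the second booster could be worse than the first by 10 points or more. For SCR307 − SCR312 it asks whether the first could be worse than the second.

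Two secondary non-inferiority decisions, Nab and IgG, rest on this. An error could go either way: an inferior second booster could be declared non-inferior, or a better one could fail. The SCR differences for hACE2 and for the updated-vaccine group would carry the wrong sign. Section 7.2.3 states no −10% criterion of its own, so for hACE2 this is a sign error and not a wrong decision.

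**Working it through.** **Inputs.** The Table 6 layout, λ and the score equations come from SAP 11.6, and the −10% margin and two-sided 95% level from 7.1, 7.2.1 and 7.2.2. The value n = 129 comes from SAP Table 2, and 100 to 150 is the planned group size. The plan gives no expected SCR, discordance rate, power or sample size for the SCR tests, so every cell count and discordance rate below is an assumption. The only sample-size figure in the plan is for the primary Nab GMR. Its N = 129 is reproduced by a paired noncentral-t calculation (SD 0.61, 90% power, margin 2/3), but nothing below depends on it.

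**Step 1: orientation.**
- π₁₊ = (a + b)/n = SCR307
- π₊₁ = (a + c)/n = SCR312
- λ = π₁₊ − π₊₁ = (b − c)/n = SCR307 − SCR312

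The numerator b − c − nλ has the same sign. If (L, U) are the limits for λ, the limits for SCR312 − SCR307 are (−U, −L). The intended rule is therefore U < +10%. Using the 11.6 lower limit unchanged gives L > −10%.

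**Step 2: one data set.** Take n = 120, a = 66, b = 30, c = 6, d = 18. Then SCR307 = 96/120 = 80% and SCR312 = 72/120 = 60%. The 11.6 quantities are A = 2n = 240, B = −36 + 216λ and C = −6λ(1 − λ), with π̂₂₁ = (√(B² − 4AC) − B)/(2A).

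| λ | B | C | π̂₂₁ | b − c − nλ | n(2π̂₂₁ + λ(1 − λ)) | score |
|---|---|---|---|---|---|---|
| −0.10 | −57.6 | 0.66 | 0.2279 | 36 | 41.50 | 36/√41.50 = 5.59 |
| +0.10 | −14.4 | −0.54 | 0.0861 | 12 | 31.47 | 12/√31.47 = 2.14 |

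- Unchanged rule: the score at λ = −0.10 must exceed 1.96. It is 5.59, so the rule passes.
- Intended rule: the score at λ = +0.10 must be below −1.96. It is +2.14, so the rule fails.

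Solved for both limits, 11.6 gives +20.0% (10.9 to 29.4). With b and c exchanged the result is −20.0% (−29.4 to −10.9), the exact mirror image.

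In the available text of 11.6 the square root appears to cover −B as well. That may come from PDF extraction, and no error is claimed from it. Read literally, it gives +20.0% (11.7 to 31.5), with the same sign.

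**Step 3: pass rates.** Both rules were applied to every possible (b, c) and weighted by multinomial probability. Here δ is the true SCR312 − SCR307, π₁₂ = (discordance − δ)/2 and π₂₁ = (discordance + δ)/2. For n = 129 and 30% discordant:

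| δ | pass, 11.6 unchanged | pass, intended direction |
|---|---|---|
| −10 points | 98.8% | 2.5% |
| −5 points | 87.5% | 17.9% |
| 0 | 54.2% | 54.2% |
| +10 points | 2.5% | 98.8% |

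Equal pass rates at δ = 0 do not mean equal verdicts. The rules disagree in 44.4% + 44.4% = 88.8% of data sets; both pass in 9.8% and both fail in 1.4%.

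**Step 4: range.** Over n = 100, 129 and 150 and discordance from 10% to 50%, the two rules give opposite verdicts in:
- 83.8% to 98.9% of data sets at δ = −10 points
- 59.2% to 95.5% at δ = −5 points
- 11.1% to 92.7% at δ = 0

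At δ = 0 and 5% discordance the conflict falls to 9.4%, 2.7% and 0.9% for n = 100, 129 and 150.

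The rules always agree when b = c. With n = 120, b = c = 18 gives −9.99% to +9.99% (both pass), and b = c = 25 gives −11.6% to +11.6% (both fail).

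**The case against.** The best defence is that 7.1 and 7.2 set the estimand and write its direction out, while 11.6 only supplies a method and contains no decision rule. On that reading a competent programmer reports SCR312 − SCR307 and negates the limits, which loses nothing. A mistake should also be visible: the two SCRs with Clopper-Pearson intervals are to be reported, and a table showing 60% minus 80% as +20% would look wrong. The error rates depend on assumed discordance, and with few discordant pairs and no true difference the two rules seldom conflict.

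Much of this stands. The intended direction is clear, the harm is conditional, and the percentages above are not forecasts. It does not remove the contradiction. Sections 7.2.1 and 7.2.2 point to 11.6 for this very interval, 11.6 is the only formula, and no section calls for negation or for a check against the separate rates. The wording for b and c does not settle the matter either, since it speaks of before and after a booster dose and names neither study. Two programmers coding independently from 11.6 could make the same error and agree with each other.

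**Conclusion.** The plan contradicts itself. The margins in Table 6, the definition of λ and the numerator of the score equation all give SCR307 − SCR312, while the rules that rely on them are stated for SCR312 − SCR307. The 11.6 interval is valid for the difference it defines; only the orientation is wrong.

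Used unchanged, it reverses the Nab and IgG SCR non-inferiority tests. At the margin itself (n = 129, 30% discordant, assumed), the chance of a false claim rises from 2.5% to 98.8%. How often the verdict would change in practice depends on discordance and a true difference that the documents do not give. The primary GMR test and the sample size are not affected. Because two stated secondary decisions depend on the formula, this must be corrected.

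**What to change.** Make one of two changes in SAP 11.6.

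1. **Redefine the difference.** Set λ = π₊₁ − π₁₊ = π₂₁ − π₁₂ = (c − b)/n and exchange b and c throughout: numerator c − b − nλ; π̂₁₂ in place of π̂₂₁; A = 2n; B = −b − c + (2n − c + b)λ; C = −bλ(1 − λ).
2. **Keep λ = SCR307 − SCR312** with limits (L, U), and state that the limits for SCR312 − SCR307 are (−U, −L), so that non-inferiority requires U < +10%.

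Either way, name Study 307 and Study 312 in the definitions of b and c. Test the program on a = 66, b = 30, c = 6, d = 18; it must return SCR312 − SCR307 = −20.0% (−29.4 to −10.9).

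The cost is SAP wording and one program check. No data or participants are involved.

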13 APPENDICES

13.1 Appendix 1: Schedule of Events

Table 7: Schedule of Events

Study Day	-30 to 1 ¹	1 ¹	8	29	Unscheduled Visit	61	91	121	151	181
Window (days)	--	-	+ 3	+ 4	--	± 7	± 15	± 15	± 15	± 15
Study Visit	Screening	1	2	3		Phone Call	Phone Call	Phone Call	Phone Call	EOS Phone Call
Informed consent	X									
Medical history ²	X				X					
Inclusion/exclusion criteria ³	X	X ⁴								
Demographics	X									
Prior/concomitant medications ⁵	X	X ⁴	X	X	X	X	X	X	X	X
Vital sign measurements	X	X ⁴			X					
Urine pregnancy test (WOCBP)	X	X ⁴								
Physical examination ⁶	X	X ⁴			X ⁷					
Baseline ECG		X ⁴								
Nasal swab at clinic for SARS-CoV-2 (PCR) – anterior nares		X ⁴								
Blood sample for anti-NP testing		X ⁴		X						
Blood sampling for SARS-CoV-2 (ELISA for anti S-protein serology, neutralizing antibody titers, and hACE2 receptor-binding inhibition assay)		X ⁴		X						
Vaccination		X ⁸								
Reactogenicity and diary collection		X ^{8,9}	X ⁹							

Table 7: Schedule of Events

Study Day	-30 to 1 ¹	1 ¹	8	29	Unscheduled Visit	61	91	121	151	181
Window (days)	--	-	+ 3	+ 4	--	± 7	± 15	± 15	± 15	± 15
Study Visit	Screening	1	2	3		Phone Call	Phone Call	Phone Call	Phone Call	EOS Phone Call
SAEs	X	X	X	X	X	X	X	X	X	X
All unsolicited AEs		X	X	X	X					
MAAEs and AESIs (including PIMMCs, myocarditis or pericarditis)		X ¹⁰	X ¹⁰	X ¹⁰	X ^{10,11}	X ¹¹				
EOS form ¹²										X

Abbreviations: AESI = adverse event(s) of special interest; eCRF = electronic case report form; EDC = electronic data capture; ELISA = enzyme-linked immunosorbent assay; EOS = end of study; hACE2 = human angiotensin-converting enzyme 2; MAAE = medically attended adverse event; PCR = polymerase chain reaction; PIMMC = potential immune-mediated medical conditions; S = spike (protein); SAE = serious adverse event; SARS-CoV-2 = severe acute respiratory syndrome coronavirus 2; WOCBP = women of childbearing potential.

¹ The Screening visit and Day 1 visit should be combined if feasible at any given study site.

² Significant medical history should be recorded, focusing on ongoing medical conditions.

³ Specific exclusions to study vaccination will be assessed before vaccination. Waivers to enrolling participants with exclusions will not be given.

⁴ Performed prior to study vaccination.

⁵ Recent (≤ 90 days) and current medications, including non-COVID-19 vaccines, should be recorded in the concomitant medication electronic case report form (eCRF). All COVID-19 vaccines administered prior to Screening should be recorded in the vaccine history eCRF. Do not record herbals, vitamins, and/or supplements. All assessments should be performed prior to vaccination. After Day 29, record all COVID-19 vaccines and only record concomitant medications and other vaccines that have caused or are used to treat an AE.

⁶ Examination at Screening to include height and weight; cervical and axillary lymph nodes, heart and any other symptom-directed (targeted) examination.

⁷ A targeted physical examination should be performed as needed.

⁸ On vaccination day, participants will remain in the clinic or under study staff observation for at least 15 minutes post-vaccination to be monitored for any immediate hypersensitivity reactions.

⁹ Reactogenicity (solicited adverse events related to vaccination) will be recorded by participants via diary on Days 1-7. The diary will be collected from the participant at the Day 8 visit and will be used to populate reactogenicity data in EDC. Should any reactogenicity event extend beyond 7 days after vaccination (toxicity grade ≥ 1), then it will be recorded as an AE with the same start date as the reactogenicity event and followed to resolution.

¹⁰ All MAAEs and all AESIs (including potential immune-mediated medical conditions [PIMMCs] and myocarditis or pericarditis) will be recorded. See [SAP Appendix 4 \(Table 11\)](#) for symptoms of myocarditis or pericarditis and [Study 312 Protocol Table 4](#) for instructions for follow-up.

¹¹ MAAEs attributed to study vaccine and all AESIs (including PIMMCs and myocarditis or pericarditis) will be recorded. See [SAP Appendix 4 \(Table 11\)](#) for symptoms of myocarditis or pericarditis and [Study 312 Protocol Table 4](#) for instructions for follow-up.

¹² EOS form will be completed for all participants, including participants who are terminated early.

13.2 Appendix 2: Listings of Adverse Events of Special Interest

Because it has been hypothesized that immunizations with or without adjuvant may be associated with autoimmunity, regulatory authorities have requested that Novavax instruct investigators to be especially vigilant regarding the PIMMC listed below (Table 8). Note that this regulatory request is not specific to Novavax's SARS-CoV-2 rS or Matrix-M adjuvant; and there is no current evidence to suggest that the study vaccines in this protocol are, or are not, associated with these illnesses. The list is not intended to be exhaustive, nor does it exclude the possibility that other diagnoses may be AESI.

Table 8: Potential Immune-Mediated Medical Conditions

Categories	Diagnoses (as MedDRA Preferred Terms)
Neuroinflammatory Disorders:	Acute disseminated encephalomyelitis (including site-specific variants: eg, non-infectious encephalitis, encephalomyelitis, myelitis, myeloradiculomyelitis), cranial nerve disorders including paralyses/paresis (eg, Bell's palsy), generalized convulsion, Guillain-Barre syndrome (including Miller Fisher syndrome and other variants), immune-mediated peripheral neuropathies and plexopathies (including chronic inflammatory demyelinating polyneuropathy, multifocal motor neuropathy and polyneuropathies associated with monoclonal gammopathy), myasthenia gravis, multiple sclerosis, narcolepsy, optic neuritis, transverse myelitis, uveitis.
Musculoskeletal and Connective Tissue Disorders:	Antisynthetase syndrome, dermatomyositis, juvenile chronic arthritis (including Still's disease), mixed connective tissue disorder, polymyalgia rheumatic, polymyositis, psoriatic arthropathy, relapsing polychondritis, rheumatoid arthritis, scleroderma (including diffuse systemic form and CREST syndrome), spondyloarthritis (including ankylosing spondylitis, reactive arthritis [Reiter's Syndrome] and undifferentiated spondyloarthritis), systemic lupus erythematosus, systemic sclerosis, Sjogren's syndrome.
Vasculitis	Large vessels vasculitis (including giant cell arteritis such as Takayasu's arteritis and temporal arteritis), medium sized and/or small vessels vasculitis (including polyarteritis nodosa, Kawasaki's disease, microscopic polyangiitis, Wegener's granulomatosis, Churg–Strauss syndrome [allergic granulomatous angiitis], Buerger's disease [thromboangiitis obliterans], necrotizing vasculitis and ANCA-positive vasculitis [type unspecified], Henoch–Schonlein purpura, Behcet's syndrome, leukocytoclastic vasculitis).
Gastrointestinal Disorders:	Crohn's disease, celiac disease, ulcerative colitis, ulcerative proctitis.
Hepatic Disorders:	Autoimmune hepatitis, autoimmune cholangitis, primary sclerosing cholangitis, primary biliary cirrhosis.
Renal Disorders:	Autoimmune glomerulonephritis (including IgA nephropathy, glomerulonephritis rapidly progressive, membranous glomerulonephritis, membranoproliferative glomerulonephritis, and mesangioproliferative glomerulonephritis).
Cardiac Disorders:	Autoimmune myocarditis/cardiomyopathy. Myocarditis and/or pericarditis

Table 8: Potential Immune-Mediated Medical Conditions

Categories	Diagnoses (as MedDRA Preferred Terms)
Skin Disorders	Alopecia areata, psoriasis, vitiligo, Raynaud's phenomenon, erythema nodosum, autoimmune bullous skin diseases (including pemphigus, pemphigoid and dermatitis herpetiformis), cutaneous lupus erythematosus, morphea, lichen planus, Stevens-Johnson syndrome, Sweet's syndrome.
Hematologic Disorders:	Autoimmune hemolytic anemia, autoimmune thrombocytopenia, antiphospholipid syndrome, thrombocytopenia.
Metabolic Disorders:	Autoimmune thyroiditis, Grave's or Basedow's disease, new onset Hashimoto thyroiditis, diabetes mellitus type 1, Addison's disease.
Other Disorders:	Goodpasture syndrome, idiopathic pulmonary fibrosis, pernicious anemia, sarcoidosis.

Abbreviations: ANCA = anti-neutrophil cytoplasmic antibody; IgA = immunoglobulin A; MedDRA = Medical Dictionary for Regulatory Activities.

Source: [DaSilva 2013](#)

Complications specific to COVID-19 are listed below ([Table 9](#)). The list is not intended to be exhaustive, nor does it exclude the possibility that other diagnoses may be AESI.

Table 9: Adverse Events Representing Complications Specific to of COVID-19 ¹

Categories	Diagnoses (as MedDRA System Organ Class/Preferred Term)
Respiratory/Infectious Disorders:	ARDS, pneumonitis, septic shock-like syndrome.
Cardiac Disorders:	Acute cardiac injury, arrhythmia.
Coagulopathy	Deep vein thrombosis, myocardial infarction, stroke.
Renal Disorders:	Acute kidney injury.
Hematologic Disorder	Thrombocytopenia, septic shock-like syndrome.
Inflammatory Disorders:	Cytokine Release Syndrome related to COVID-19 infection ² , multisystem inflammatory syndrome in children (MIS-C).
Neurologic Disorders:	Generalized convulsions.

Abbreviations: ARDS = acute respiratory distress syndrome; COVID-19 = coronavirus disease 2019; DAIDS = Division of AIDS; MedDRA = Medical Dictionary for Regulatory Activities.

¹ COVID-19 manifestations associated with more severe presentation and decompensation with consideration of enhanced disease potential. The current listing is based on Coalition for Epidemic Preparedness Innovations /Brighton Collaboration Consensus Meeting (12/13 March 2020) and expected to evolve as evidence accumulates ([Lambert 2020](#)).

² Cytokine release syndrome related to COVID-19 infection is a disorder characterized by nausea, headache, tachycardia, hypotension, rash, and/or shortness of breath ([DAIDS 2017](#)).

13.3 Appendix 3: Toxicity Grading Scale for Clinical Abnormalities, (local and general systemic reactogenicity, clinical laboratory, and vital signs)

Table 10: Modified FDA Toxicity Grading Scale for Clinical Abnormalities (Local and General Systemic Reactogenicity)

Local Reaction to Injectable Product				
	Mild (Grade 1)	Moderate (Grade 2)	Severe (Grade 3)	Potentially Life Threatening (Grade 4)
Pain	Does not interfere with activity	Repeated use of non-prescription pain reliever > 24 hours or interferes with activity	Significant; any use of prescription pain reliever or prevents daily activity	Requires ER visit or hospitalization
Tenderness	Mild discomfort to touch	Discomfort with movement	Significant discomfort at rest	Requires ER visit or hospitalization
Erythema/redness ^a	2.5 – 5 cm	5.1 – 10 cm	> 10 cm	Necrosis or exfoliative dermatitis ^b
Induration/swelling ^a	2.5 – 5 cm	5.1 – 10 cm	> 10 cm	Necrosis ^b
Systemic (General)				
	Mild (Grade 1)	Moderate (Grade 2)	Severe (Grade 3)	Potentially Life Threatening (Grade 4)
Fever ^c (°C) (°F)	38.0 – 38.4 100.4 – 101.1	38.5 – 38.9 101.2 – 102.0	39.0 – 40 102.1 – 104	> 40 > 104
Nausea/vomiting	Does not interfere with activity or 1 – 2 episodes/24 hours	Some interference with activity or > 2 episodes/24 hours	Prevents daily activity, or requires IV hydration outside of hospital	Requires ER visit or hospitalization
Headache	Does not interfere with activity	Repeated use of non-prescription pain reliever > 24 hours or interferes with activity	Significant; any use of prescription pain reliever or prevents daily activity	Requires ER visit or hospitalization
Fatigue/Malaise	Does not interfere with activity	Some interference with activity	Significant, prevents daily activity	Requires ER visit or hospitalization
Myalgia	Does not interfere with activity	Some interference with activity	Significant, prevents daily activity	Requires ER visit or hospitalization
Arthralgia	Does not interfere with activity	Some interference with activity	Significant, prevents daily activity	Requires ER visit or hospitalization

^a The measurements should be recorded as a continuous variable.

^b These events are not participant reported through the diary and will be monitored through the AE pages of the study database.

^c Oral temperature if participant collected, sites may collect temperature using local clinic practices/devices. Toxicity grade will be derived.

Source: [FDA 2007](#)

